**Primary Outcome Measure:**

*Cumulative duration*

*Cumulative duration of one or more deviations in vital signs. List of vital signs, and normal limits detailed in protocol, whichever comes first.*

Vital signs value deviations are calculated per 24 hours of monitoring time.

*[Time Frame: First 5 days from randomization or until discharge]*

**Secondary Outcome Measures:**

- *Frequency of sustained deviation alerts*

*Frequency of each of the sustained deviations in vital signs. List of vital signs, and normal limits detailed in protocol.*

Number of alarms are calculated as the number of alarms per 24 hours.

*[Time Frame: First 5 days from randomization or until discharge, whichever comes first]*

- *AE during the first 7 days and the first 30 days*
- *SAE during the first 7 days and the first 30 days*

**Tertiary Outcome Measures:**

1. *Length of hospital stay*

*Length of hospital stay*

*[Time Frame: 30 days from randomization and 6 months]*

2. *Patient related post-admission healthcare expenses*

*Total patient-related healthcare expenses in patients experiencing adverse clinical outcomes compared to patients without such outcomes and the effect of the study intervention on expenses*

*[Time Frame: 2 years]*

3. *Staff response time (intervention group only)*

*Time from the staff is notified by app, until they respond by selecting 'check on patient' in app*

*Stratified according to time of day*

*[Time Frame: Up to 5th postoperative day or until discharge, whichever comes first]*

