### **Outcome analysis:**

- *Intention to treat analysis*
  - Patient outcomes are analyzed based on the randomization groups.
- *Per-protocol analysis*
  - Patients included in the intervention are those with:
    - intervention patients with alerts with at least one registered use of the app in relation to an alert, as indicated if the “attend”, “postpone/snooze” or “transfer” buttons have been used.
  - OR
  - intervention patients with no alerts, are also included in the intervention group.

AND

- at least 12 hours of monitoring with valid data transfer.
- Patients in the control-group are all patients from the control group with at least 12 hours of monitoring.

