### **Data analysis:**

- Vital values: Gaps in vital value data were not imputed.  
Durations will be calculated in minutes per 24 hours (1440 minutes) of monitoring.
- Data will be presented with descriptive statistics.  
Categorical data will be tested with Fishers exact test.  
Continuous data will be tested with Wilcoxon Mann-Whitney U test.  
Time-till-event will be tested with cox-regression.
- For statistical tests and alpha of < 0.05 will be considered statistically significant.

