**Table 1: Patient demographics**

	Control arm N = 200	Intervention arm N = 200
Age, mean		
Male, no (%)		
ASA class		
I		
II		
III		
>IV		
Smoking status		
Never smoked		
Former smoker		
Current smoker		
Pack years for former and current smokers (mean)		
Preexisting conditions, n (%)		
COPD		
Vascular insufficiency		
Chronic arterial hypertension		
Diabetes Mellitus		
Type of surgery		
Abdominal		
Vascular		
Urologic		
Orthopedic		

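### Two-year expenses are to be compared by adverse-outcome status, an observational split, and the only method the SAP gives for continuous data is an unadjusted rank test

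*SAP*

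**What the plan says.** Under Tertiary Outcome Measures, item 2 puts two comparisons into one sentence. The first is "Total patient-related healthcare expenses in patients experiencing adverse clinical outcomes compared to patients without such outcomes". The second is "the effect of the study intervention on expenses". Both carry "Time Frame: 2 years".

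Three other places bear on how the first comparison would be analysed:

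- Data analysis chooses tests by type of data: "Continuous data will be tested with Wilcoxon Mann-Whitney U test". Results are judged by the rule that an "alpha of < 0.05 will be considered statistically significant". No method specific to expenses is given, and no adjusted method that would apply to them.
- Outcome analysis, on intention to treat, states "Patient outcomes are analyzed based on the randomization groups". That serves the second comparison but cannot serve the first, whose groups are not the arms.
- Table 1 lists age, ASA class, smoking, "Preexisting conditions, n" (%) and type of surgery. Their only stated use is to describe the arms.

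**The concern.** Patients with and without an adverse outcome are sorted by something that happens after randomisation. They can be expected to differ at baseline. Higher ASA class, COPD, vascular insufficiency and diabetes plausibly make an adverse outcome more likely, and they also generate healthcare cost over 2 years whether or not one occurs. A rank test between the two groups cannot separate the two sources of cost.

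At stake is the reading of one reported contrast. A difference in expenses could appear, and could be statistically significant with 400 patients, even if adverse outcomes added nothing to cost. The issue is who is compared. It is separate from whether a rank test is a good way to compare cost between the randomised arms.

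**Working it through.** The SAP states no expected expense, effect size or power for this objective, so there is no figure to reproduce. What can be checked is the mechanism and how far its size depends on inputs the document does not give.

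**Inputs from the SAP.** The table shells give "Control arm N = 200" and the same for the intervention arm, so 400 in total; alpha is 0.05.

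**Inputs assumed.** A share p = 0.30 of patients have high baseline risk. Adverse-outcome risk is r1 in these and r0 in the others. Two-year cost is k times as high in high-risk patients. The adverse outcome itself adds no cost.

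**Step 1: apparent ratio of mean cost.**

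- High-risk share among patients with an adverse outcome: s1 = p·r1 / [p·r1 + (1 − p)·r0]
- High-risk share among the rest: s0 = p(1 − r1) / [p(1 − r1) + (1 − p)(1 − r0)]
- Apparent cost ratio: [1 + (k − 1)s1] / [1 + (k − 1)s0]

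Worked case, r0 = 0.15, r1 = 0.40, k = 2:

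- s1 = 0.12 / (0.12 + 0.105) = 0.12 / 0.225 = 0.533
- s0 = 0.18 / (0.18 + 0.595) = 0.18 / 0.775 = 0.232
- ratio = 1.533 / 1.232 = 1.24

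The same formulas over a range of assumptions:

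| r0 | r1 | k | s1 | s0 | Apparent ratio |
|---|---|---|---|---|---|
| 0.20 | 0.20 | any | 0.300 | 0.300 | 1.00 |
| 0.20 | 0.30 | 1.25 | 0.391 | 0.273 | 1.03 |
| 0.15 | 0.30 | 1.5 | 0.462 | 0.261 | 1.09 |
| 0.15 | 0.40 | 2 | 0.533 | 0.232 | 1.24 |
| 0.15 | 0.50 | 3 | 0.588 | 0.201 | 1.55 |

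The true ratio is 1.00 in every row.

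**Step 2: effect on the test.** A simulation used 400 patients, log-normal costs with log-SD 1, p = 0.30, k of 1.25, 1.5 and 2, no true cost of an adverse outcome, and 1,500 runs per scenario. The rejection rates at 0.05 should be 5 %. The Monte Carlo standard error at 5 % is √(0.05 × 0.95 / 1500) = 0.6 percentage points. Ranges are over the three values of k.

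| r0 v r1 | Mann-Whitney by adverse outcome | Geometric cost ratio | Adjusted log-cost regression | Mann-Whitney by arm |
|---|---|---|---|---|
| 20 % v 20 % | 4.7–5.0 % | 1.00 | 5.0–5.5 % | 4.9–5.1 % |
| 20 % v 30 % | 5.9–9.3 % | 1.03–1.08 | 5.1–5.9 % | 4.4–4.8 % |
| 20 % v 40 % | 6.0–22.6 % | 1.05–1.16 | 4.3–5.0 % | 3.9–4.3 % |
| 15 % v 45 % | 9.6–48.9 % | 1.08–1.27 | 4.7–5.6 % | 4.3–4.9 % |

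The highest ratio here (1.27) is below the 1.55 of Step 1 mainly because k stops at 2 rather than 3 and r1 at 0.45 rather than 0.50; it is also a ratio of geometric means.

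**Reading.** With no link between baseline illness and adverse outcomes, the unadjusted test behaves properly. With a weak link the distortion is slight, and with a strong link it is large. The comparison by arm holds its level throughout. Adjustment restores the level, but in this simulation the confounder is single and perfectly measured, which is more favourable than practice.

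**The case against.** The strongest reply is that the SAP makes no causal claim here. It says only that expenses in one group are compared with those in the other, and it attaches the word effect solely to the randomised part. A reader might infer that the plan counts the cost of prior illness as the cost of adverse outcomes; the wording does not support that. If the contrast is meant as description, the harm is one of interpretation. This stands. What remains is that the contrast shares a sentence with the intervention's effect and is not marked as observational.

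A reader might also infer that the contrast supplies the value of an avoided adverse outcome and so the economic case for monitoring. The SAP contains no cost-effectiveness model, savings calculation or value per event, and it names a direct comparison of expenses by arm. That inference is unsupported.

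Third, the unadjusted test comes from a general rule by data type. Table 4, for tertiary outcomes, has no expense row, no columns by adverse-outcome status and no p-values, so the SAP nowhere shows this contrast being tested. That is fair, but the general rule is the only one for continuous data, and following it gives the unadjusted test.

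Fourth, the size is assumed throughout, and inputs can be picked to make it look large; the tables therefore start at no bias. The direction is not certain either, since early death shortens the time over which cost accrues. Finally, Table 1 records the type of surgery and not its extent, so extent can be neither cited from that table nor adjusted for with it.

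**Conclusion.** The point holds as a minor one. Following the SAP as written gives a comparison of 2-year expenses that is open to confounding by baseline illness, with no adjusted method provided. On assumed inputs the spurious excess in mean cost lies anywhere between zero and about 55 %, and the false-positive rate between about 5 % and 49 %. These figures rest on an assumed 30 % high-risk share, assumed risks and cost ratios, and an adverse outcome that adds no cost. Only the 400 patients and the 0.05 level come from the SAP.

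The reach is narrow: one part of one tertiary outcome. The expense comparison by randomised arm and the primary and secondary outcomes are not touched.

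**What to change.** Split item 2 of the tertiary outcomes into two questions.

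1. **Expenses by randomised arm.** Report this separately, as the only estimate of effect.
2. **Expenses by adverse outcome.** Replace the rank test with a regression of 2-year cost, for example a gamma model with log link, on adverse-outcome status. Adjust for age, ASA class, type of surgery, smoking, pre-existing conditions and randomised arm. State which adverse outcomes count and in what time window (a reference to the protocol suffices if it defines them), and how deaths within the 2 years are handled. Report the adjusted difference with a 95 % CI, labelled an association subject to residual confounding.

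If only a description is wanted, dropping the significance test and labelling the contrast observational would answer the problem of interpretation, though not the confounding.

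The cost is a change of wording and one extra model on variables already listed in Table 1. The reported excess cost will probably be smaller than the unadjusted figure.

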### **Outcome analysis:**

- *Intention to treat analysis*
  - Patient outcomes are analyzed based on the randomization groups.
- *Per-protocol analysis*
  - Patients included in the intervention are those with:
    - intervention patients with alerts with at least one registered use of the app in relation to an alert, as indicated if the “attend”, “postpone/snooze” or “transfer” buttons have been used.
  - OR
  - intervention patients with no alerts, are also included in the intervention group.

AND

- at least 12 hours of monitoring with valid data transfer.
- Patients in the control-group are all patients from the control group with at least 12 hours of monitoring.

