**Table 4: Tertiary outcomes**

	Intention to treat analysis		Per protocol analysis	
	Control arm N = 200	Intervention arm N = 200	Control arm N = 280	Intervention arm N = 120
Serious Adverse Events at 7 days / n (%)	XX (xx %)	XX (xx %)	XX (xx %)	XX (xx %)
Serious Adverse Events at 30 days / n (%)	XX (xx %)	XX (xx %)	XX (xx %)	XX (xx %)
Death / n (%)	XX (xx %)	XX (xx %)	XX (xx %)	XX (xx %)
Length of stay / days [IQR]	X [X-XX]	X [X-XX]	X [X-XX]	X [X-XX]
Reoperation / n (%)	XX (xx %)	XX (xx %)	XX (xx %)	XX (xx %)

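### Table 4's per-protocol column sizes (280 control, 120 intervention) cannot come from the SAP's per-protocol rule, and that rule excludes on post-randomisation events in one arm only

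*SAP*

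**What the plan says.** The Outcome analysis section of the SAP defines intention to treat by randomised group and then gives a per-protocol rule. In the intervention arm the rule keeps "intervention patients with alerts with at least one registered use of the app in relation to an alert", and "intervention patients with no alerts, are also included in the intervention group". Both kinds of patient must also have "at least 12 hours of monitoring with valid data transfer". For the other arm the rule reads "Patients in the control-group are all patients from the control group with at least 12 hours of monitoring". Nothing in the section moves a patient from one arm to the other.

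Table 4 has two pairs of columns. The intention-to-treat pair is headed 200 and 200. The per-protocol pair is headed "Control arm N = 280" and "Intervention arm N = 120". The rows are serious adverse events (SAE) at 7 and 30 days, death, length of stay and reoperation.

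The alerts that decide who faces the app-use condition arise after randomisation. They are closely tied to a listed secondary outcome, "Frequency of each of the sustained deviations in vital signs", which Table 3 compares between arms using theoretical alarms for controls.

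**The concern.** There are two separate problems, of unequal certainty.

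The first is a contradiction. A rule that only removes patients cannot enlarge the control arm, yet the table shows it enlarged. An analyst who follows the text drops intervention patients without app use. An analyst who fills the table as headed would have to count 80 of them as controls. Both results could be reported as per protocol, and they compare different patients.

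The second is selection. Whether an alerted intervention patient stays in the set depends on an alert having fired and on staff having pressed a button, both after randomisation. No such condition thins the control arm. If the excluded patients differ in risk from the rest of their arm, the two per-protocol columns will differ even when the intervention does nothing. The SAP does not say that this analysis is only supportive of intention to treat.

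**Working it through.** **Check of the printed N**

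Inputs: 200 randomised per arm (intention-to-treat columns of Table 4, also Tables 1 to 3); per-protocol 280 and 120 (Table 4); the rule in Outcome analysis.

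- Largest control N under the rule: 200, reached if every control has 12 hours of monitoring. Printed: 280, an excess of 280 - 200 = 80. The plan's figure is not reproduced.
- Intervention N: 120 alone is possible, if 200 - 120 = 80 patients are dropped. The columns would then be at most 200 and 120, a total of at most 320.
- Printed total: 280 + 120 = 400 = 200 + 200, so the table drops nobody.
- Moving 80 patients from intervention to control gives 200 - 80 = 120 and 200 + 80 = 280, an exact match. That is an as-treated comparison.

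**Illustration of the selection effect**

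The SAP gives no alert, non-use or event rates, so all rates here are assumptions. Take 200 per arm, no treatment effect, and 70% of patients alerted (140 alerted, 60 not). Let 30-day SAE risk be 30% with an alert (42 events) and 10% without (6 events). Controls then have 48/200 = 24.0%.

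Let E alerted intervention patients without app use be excluded, with SAE risk r. Under the written rule:

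intervention proportion = (48 - E × r) / (200 - E), against 48/200 in controls.

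| E | Non-use among alerted, E/140 | r = 30% | Shift (points) | r = 15% | Shift (points) |
|---|---|---|---|---|---|
| 14 | 10% | 43.8/186 = 23.5% | -0.5 | 45.9/186 = 24.7% | +0.7 |
| 20 | 14% | 42/180 = 23.3% | -0.7 | 45/180 = 25.0% | +1.0 |
| 40 | 29% | 36/160 = 22.5% | -1.5 | 42/160 = 26.3% | +2.3 |
| 80 | 57% | 24/120 = 20.0% | -4.0 | 36/120 = 30.0% | +6.0 |

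- With r = 24%, the arm average, the shift is zero at any E.
- The two-sided Fisher p-values for the last row are 0.49 and 0.24; 0.24 is the smallest in the table.
- The 30.0% cell is extreme. It implies (42 - 12)/(140 - 80) = 30/60 = 50% risk in the remaining alerted patients.
- If 90% of patients are alerted, controls have (54 + 2)/200 = 28.0%. With r = 30% the intervention column is 27.8%, 27.5% and 26.7% for E = 20, 40 and 80, a shift of at most -1.3 points.

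**The same 80 patients moved instead of dropped**

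intervention (48 - 80r)/120 against control (48 + 80r)/280:

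- r = 30%: 24/120 = 20.0% against 72/280 = 25.7%, gap -5.7 points (Fisher p = 0.25). Dropping gives -4.0.
- r = 15%: 36/120 = 30.0% against 60/280 = 21.4%, gap +8.6 points (Fisher p = 0.07). Dropping gives +6.0.

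On the same assumed data, the two readings give different answers.

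**The case against.** Table 4 is an empty shell, so 280 and 120 may be illustrative, and the only written rule is explicit about where controls come from. That is fair as far as intent goes. A reader might infer from the exact fit that an as-treated analysis is planned; the document does not support this, since no text describes moving patients. What stands is the contradiction: the cells of the table are marked with X's, whereas the column sizes are specific numbers that the rule cannot give.

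On selection, restricting a per-protocol set to patients who received the intervention is common. The app belongs to one arm, so its use cannot be observed in controls and no true counterpart exists. Matching controls on theoretical alarms alone would not fully remove the selection. The 12-hour requirement does apply to both arms, and the extra words on valid data transfer for the intervention arm may be loose drafting. The per-protocol columns appear only in Table 4, beside the intention-to-treat columns, with no p-value column, although the general rule in Data analysis ("Categorical data will be tested with Fishers exact test") could still be applied to them. All of this limits the weight of the point. None of it makes the comparison free of selection.

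Two stronger readings are tempting. One is that the rule favours the intervention. The sign depends on whether excluded patients carry more or less risk than the arm average, and the SAP gives nothing to settle that. The other is that the app-use condition must be removed. It serves a legitimate adherence question, and dropping it would bring the set close to intention to treat.

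**Conclusion.** The contradiction is certain and needs no assumption: at most 200 per-protocol controls are possible, 280 are printed, and the excess of 80 equals the shortfall in the intervention column. The Outcome analysis text and Table 4 must be reconciled before analysis.

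The selection problem is real in kind but unknown in size and direction. Under the assumed rates it is under 1 point when 10% of alerted patients have no app use, and it disappears if excluded patients carry average risk. It reaches -4.0 to +6.0 points only if 80 patients are dropped, a number taken from the disputed column size. No scenario, dropped or moved, gives p < 0.05. It therefore calls for a caveat and clear reporting.

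The point is confined to the per-protocol columns of Table 4. The intention-to-treat analysis and the primary comparison in Table 2 are unaffected. This should be fixed, but it does not threaten the trial's main result.

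**What to change.** 1. Correct the per-protocol column sizes in Table 4 to agree with the rule: control at most 200, with excluded intervention patients dropped and not moved. If the sizes are not yet known, leave them blank.
2. State that per-protocol patients are analysed in their randomised arm.
3. Apply one monitoring criterion, 12 hours with valid data, in the same words to both arms.
4. Label the per-protocol analysis supportive of intention to treat. Note that membership depends on alerts and app use after randomisation in one arm only.
5. Report how many alerted intervention patients were excluded for having no registered app use.

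Optionally, add a sensitivity analysis on a set defined only by the common 12-hour criterion, with app use among alerted patients reported as adherence. It need not replace the present rule. Monitoring time is itself post-randomisation, so some selection can remain there too.

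The cost is a few lines of SAP wording, two numbers in a table shell, and a valid-data check in controls.

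### The per-protocol set applies a data-validity condition to its 12-hour minimum in the intervention arm but not in the control arm

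*SAP*

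**What the plan says.** The Outcome analysis section of the SAP sets separate per-protocol entry rules for the two arms.

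- **Intervention.** The patient either had no alerts or belongs to the group described as "intervention patients with alerts with at least one registered use of the app in relation to an alert". In addition, joined by a capitalised AND, the patient must have "at least 12 hours of monitoring with valid data transfer".
- **Control.** "Patients in the control-group are all patients from the control group with at least 12 hours of monitoring".

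Two other statements bear on how the hours might be counted. Under Primary Outcome Measure: "Vital signs value deviations are calculated per 24 hours of monitoring time". Under Data analysis: "Gaps in vital value data were not imputed". Neither says whether a stretch without usable signal counts as monitoring.

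**The concern.** Both arms have the same 12-hour threshold, but the quantity that must reach it is worded differently. The control sentence is complete in itself and restates its own threshold, so the validity condition reads as part of the intervention rule only.

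Data validity is observed after randomisation. A filter on such a variable that acts in one arm only makes membership of the analysis set depend on allocation. Where the patients removed differ in prognosis from those kept, the two per-protocol groups are no longer comparable even if the intervention has no effect. Table 4 is the only shell with per-protocol columns. Its outcomes (serious adverse events at 7 and 30 days, death, length of stay, reoperation) are the ones a clinical reader will look at most closely.

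This is distinct from the app-use condition. App use can only be judged in the intervention arm, so that asymmetry is partly unavoidable. The validity condition also reaches intervention patients with no alerts, whom the app-use condition does not remove.

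**Working it through.** The SAP gives no figure on this point to reproduce, so the check is mainly a comparison of text.

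**1. Apply both rules to the same patient.** Take a hypothetical patient with 20 hours monitored, of which 5 hours gave valid data, and no alerts.

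| | Intervention rule | Control rule |
|---|---|---|
| Alert/app condition | met (no alerts) | none |
| 12-hour condition | 5 h valid, below 12 h: fails | 20 h monitored, above 12 h: met |
| Per-protocol set | excluded | included |

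**2. Look for text that equalises the rules.** The primary-outcome denominator is monitoring time, not stated to be valid-data time. The statement on gaps rules out imputation but does not remove gaps from the hours counted. Nothing else in the SAP bears on it.

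**3. Ask whether one rule could serve both arms.** Table 2 reports durations for control patients, and Table 3 reports the alarms a system would theoretically have issued for them. Control vital signs are therefore recorded, and hours of valid recording can be counted in both arms.

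**4. Try to size the effect from the SAP.** The Table 4 per-protocol headers are "Control arm N = 280" and "Intervention arm N = 120". These sum to 280 + 120 = 400, the same as 200 + 200 under intention to treat, so they show no net exclusions. The control column is 280 − 200 = 80 larger and the intervention column 200 − 120 = 80 smaller. That looks like patients moved between arms, which the Outcome analysis section does not provide for. The headers cannot be used to size this problem.

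**5. Show what the bias would depend on.** Let f be the share of each arm with at least 12 h monitored but under 12 h valid, r1 the event risk in those patients and r0 the risk in the rest. Assume no treatment effect and ignore the app-use condition. Then:

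- intervention per-protocol risk = r0
- control per-protocol risk = (1 − f) × r0 + f × r1
- control minus intervention = f × (r1 − r0)

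The values below are assumptions, none from the SAP, chosen only to show how the sign behaves.

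| f | r0 = 20%, r1 = 40%: control vs intervention | r0 = 40%, r1 = 20%: control vs intervention |
|---|---|---|
| 5% | 21% vs 20% (+1 point) | 39% vs 40% (−1 point) |
| 10% | 22% vs 20% (+2 points) | 38% vs 40% (−2 points) |
| 20% | 24% vs 20% (+4 points) | 36% vs 40% (−4 points) |

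If r1 = r0 the difference is zero. The sign is that of r1 − r0, on which the SAP is silent.

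**The case against.** The strongest reply is that valid data transfer may mean transfer to the alerting system or staff app. On that reading the phrase describes delivery of the intervention, has no control counterpart, and stops a patient from counting as alert-free merely because transfer failed. This is a natural reading, since the phrase is joined to the app-use condition. But the SAP does not say so, and on this reading the control arm still has no minimum of valid recording.

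A second reply is that monitoring in the control rule may already mean recorded time, so that the patient with 5 valid hours is excluded from both arms. That is possible. Even so, adjacent bullets use two different phrases, and an analyst following them literally would program two different filters.

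A reader might also infer that the rule favours the intervention, because deteriorating patients lose signal. The SAP does not support that direction. Repeated sensor removal fits mobile, recovering patients at least as well, and dropping them would raise the intervention arm's event rates. Patients who die or are transferred before 12 hours of monitoring fail the shared threshold in both arms.

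The limits on size and reach also stand. At an assumed 20% risk with 200 per arm, the standard error of a difference is √(2 × 0.20 × 0.80 / 200) = 0.04, or 4 points, so shifts of 1 or 2 points would be small beside sampling error. Table 2 is headed for intention to treat only, Table 3 has no per-protocol columns, and Table 4 has no p-value column.

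**Conclusion.** The imbalance holds on the wording of the SAP: read literally, a post-randomisation data-validity filter acts in one arm only. It biases the Table 4 per-protocol comparison if data loss is related to outcome. How many patients are affected, and in which direction, cannot be determined from the document, so neither a spurious benefit nor any particular number of percentage points should be claimed.

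The conclusion assumes that monitoring can include time without valid data. A protocol definition that excludes such time would remove the imbalance, and the SAP should then refer to it.

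The weight is moderate. It concerns a secondary analysis set, and the primary outcome as laid out in Table 2 is untouched. It is nevertheless a rule to change and not just a missing detail, because a common criterion is available from data the trial already needs.

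**What to change.** 1. Define valid monitoring time once, as the hours with valid recorded vital-sign data, and state how validity is judged.
2. Require at least 12 such hours in both arms, computed from the recorded files by the same algorithm.
3. If valid data transfer was meant as delivery of alerts to the staff app, state it as a separate intervention-delivery criterion beside the app-use condition. Keep the common 12-hour minimum of valid data in both arms.
4. Label the per-protocol results as supportive only. The app-use condition remains specific to the intervention arm and is also post-randomisation, so harmonising the 12-hour rule does not make the groups fully comparable.
5. Reconcile the Table 4 per-protocol headers with the entry rules.

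The cost is a few sentences in the SAP and a slightly smaller control per-protocol group. The common threshold needs no new data, since control recordings already feed Tables 2 and 3. A separate delivery criterion would need a record of transfer to the app, which the SAP does not describe.

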**Table 2: Primary outcomes - Cumulative duration of deviating vital values per 24 hours**

	Intention to treat analysis		
	Control arm N = 200	Intervention arm N = 200	p-value
Total cumulative			
Respiratory			
SpO 2 < 92 %			
SpO 2 < 88 %			
SpO 2 < 85 %			
SpO 2 < 80 %			
RF < 5 min 			
RF < 11 min 			
RF > 24 min 			
RF > 30 min 			
Circulatory			
HR < 30 min 			
HR [30 - 40] min 			
HR > 110 min 			
HR > 130 min 			
SBP < 70 mmHg			
SBP < 90 mmHg			
SBP > 180 mmHg			
SBP > 220 mmHg			

**Table 3: Secondary outcomes - Median number of alarms for sustained deviations per 24 hours. For control patients the number is the theoretical number of alarms a system would issue.**

	Control arm N = 200	Intervention arm N = 200	p-value
Desaturation			
SpO2 < 92 % for > 60 min			
SpO2 < 88 % for > 10min			
SpO2 < 85 % for > 5 min			
SpO2 < 80 % for > 1 min			
Bradypnea			
RF < 5 min  for > 1 min			
RF < 11 min  for > 15 min			
Tachypnea			
RF > 24 min  for > 15 min			
RF > 30 min  for > 5 min			
Bradycardia			
HR < 30 min  for > 1 min			
HR [30 - 40] min  for > 5 min			
Tachycardia			
HR > 110 min  for > 60 min			
HR > 130 min  for > 30 min			
Hypotension			
SBP < 70 mmHg for > 30 min			
SBP < 90 mmHg for > 60 min			
Hypertension			
SBP > 180 mmHg for > 60 min			
SBP > 220 mmHg for > 30 min			

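### The 12-hour monitoring condition lets an early death, or another event that ends monitoring, remove the patient from the per-protocol columns that count such events

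*SAP*

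**What the plan says.** The SAP section Outcome analysis defines two analyses. For intention to treat, "Patient outcomes are analyzed based on the randomization groups", with no monitoring minimum. For the per-protocol analysis, intervention patients must meet an app-use rule (or have had no alerts) and must also have "at least 12 hours of monitoring with valid data transfer". For the other arm, "Patients in the control-group are all patients from the control group with at least 12 hours of monitoring". Nothing is said about patients whose monitoring stopped because of an outcome event.

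Per-protocol columns appear in one place, Table 4. Its rows include "Serious Adverse Events at 7 days / n" (with a matching 30-day row), death, length of stay and "Reoperation / n". The same rows have intention-to-treat columns alongside. Under Secondary Outcome Measures the SAE window is "SAE during the first 7 days and the first 30 days", so the first 12 hours are inside it. Table 2, for the primary outcome, carries only the heading "Intention to treat analysis". Table 3 names no analysis set.

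**The concern.** Twelve hours of completed monitoring is known only after randomisation, and the outcomes being counted can prevent it. A patient who dies before that point is excluded because of the death. The same holds for an SAE or reoperation after which monitoring is not resumed. Discharge before 12 hours has a similar effect on length of stay, since it removes some of the shortest stays.

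A minimum recording time is reasonable for outcomes expressed per 24 monitored hours, where a very short recording gives an unstable rate. No row of Table 4 is such a rate. The condition is thus applied in the only table with per-protocol results, where it does not serve that purpose and can select on the outcome. At stake is how the per-protocol safety figures are read. If early losses differed between arms, those columns could show a difference that came from the selection.

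**Working it through.** **The plan's own figures.** The Table 4 shell prints per-protocol sizes of 280 (control) and 120 (intervention), against 200 and 200 for intention to treat. The stated rules do not give these numbers: the per-protocol control group is a subset of the 200 controls, so it cannot reach 280. Also 280 + 120 = 400 = 200 + 200, which leaves nobody excluded for short monitoring. The shell therefore cannot show how many patients the 12-hour rule would remove, and it conflicts with the definition.

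**Inputs.** n = 200 per arm is from the table shells. The SAP gives no event rates, so the following are assumptions for one arm:
- e = patients with the event
- k = those among them whose event ended monitoring before 12 hours
- m = patients without the event who are also dropped for under 12 hours

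**Formula.** The intention-to-treat proportion is e/n. Under the 12-hour rule alone, leaving the app-use rule aside, the per-protocol proportion is (e − k)/(n − k − m).

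**Case m = 0** (only patients with the event are dropped):

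| e/200 | k = 1 | k = 2 | k = 4 |
|---|---|---|---|
| 10/200 = 5.0% | 9/199 = 4.5% | 8/198 = 4.0% | 6/196 = 3.1% |
| 20/200 = 10.0% | 19/199 = 9.5% | 18/198 = 9.1% | 16/196 = 8.2% |
| 40/200 = 20.0% | 39/199 = 19.6% | 38/198 = 19.2% | 36/196 = 18.4% |

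The relative understatement runs from about 2% to about 39% and is largest for rare events. For deaths, e = 6 and k = 2 gives 6/200 = 3.0% against 4/198 = 2.0%.

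**Case m > 0.** The per-protocol proportion is below e/n only when m < k(n − e)/e.
- SAEs, e = 50, k = 4: the break-even is 4 × 150/50 = 12. With m = 0 the result is 46/196 = 23.5%; with m = 12 it is 46/184 = 25.0%, equal to 50/200; with m = 20 it is 46/176 = 26.1%, above it.
- Deaths, e = 6, k = 2: the break-even is 2 × 194/6 = 64.7, so 65 or more other short-monitoring patients in one arm would be needed to offset the loss.

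**Between arms.** Equal k and m with equal e give equal proportions, so no difference appears. With e = 20 in each arm, m = 0 and 4 patients lost from one arm only, 10.0% v 10.0% becomes 16/196 = 8.2% v 20/200 = 10.0% (Fisher p = 0.60). With e = 50 in each arm and losses of 6 (intervention) and 2 (control), the result is 44/194 = 22.7% v 48/198 = 24.2%, a gap of 1.6 points against a standard error of about 4.3 points.

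**The case against.** The strongest reply is that nothing vanishes from the report. Table 4 sets intention-to-treat columns beside the per-protocol ones for the same rows, and those count every event from randomisation. A reader might infer that early deaths or SAEs are hidden, but this is true of the per-protocol columns alone. The primary outcome table is not touched, and Table 4 has no p-value column. This reply stands and limits the importance of the point.

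Second, a reader might infer that any early reoperation or transfer excludes the patient. The SAP asks for 12 hours of monitoring, not for the first 12 hours and not for an unbroken run, and its monitoring outcomes extend to 5 days or discharge. A patient reoperated at hour 6 may resume monitoring and qualify. Only death, discharge or a permanent stop before 12 hours necessarily excludes. This also stands.

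Third, a reader might infer that per-protocol rates must be too low in both arms, or that the intervention gains a false safety advantage. Neither follows. Event-free patients with short recordings are dropped too, and the SAE example reaches no bias at 12 such patients. The 12-hour threshold is the same in both arms, although only the intervention rule adds valid data transfer. The documents give no evidence that losses would differ.

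Fourth, the printed 280 and 120 leave it unclear whether the exclusion operates in Table 4 at all. That is a separate inconsistency to reconcile. Correcting those sizes to match the written definition would leave the present problem in place.

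Finally, some conditioning on exposure belongs to any per-protocol set. That is so, but it does not require the outcome itself to be able to cause the exclusion.

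**Conclusion.** The point holds in limited form, as a minor one. As written, the per-protocol definition lets an early death, or an SAE or reoperation after which monitoring is not resumed, take the patient out of the columns meant to count it. The intention-to-treat results and the primary outcome table are unaffected.

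The size cannot be derived from the SAP, and every event count above is an assumption. The effect is downward for early deaths unless very many other patients in the arm also have short monitoring, and it is undetermined for SAEs. A bias between arms arises only if the losses differ by arm.

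**What to change.** For the per-protocol columns of Table 4, choose one of two rules and write it into Outcome analysis.

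- (a) Keep in the set patients who started monitoring and whose monitoring ended before 12 hours because of death or another outcome event. Continue to exclude patients never monitored and those short for other reasons.
- (b) Define a 12-hour landmark in both arms, count only events after it, and label the columns accordingly. State the clock it runs on, because 12 hours of monitoring need not be the first 12 hours.

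Under either rule, list patients with under 12 hours of monitoring by arm, with the reason and any event. Leave the 12-hour minimum unchanged for outcomes expressed per 24 monitored hours.

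Simply deleting the condition for Table 4 would not do. The definition also admits intervention patients with no alerts, so a never-monitored patient would count as treated per protocol.

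The cost is a few lines of SAP text and one short listing. Under (a) the per-protocol set differs between event outcomes and monitoring outcomes, and length of stay still omits patients discharged before 12 hours, whom the listing will show. Under (b) the columns describe only events after 12 hours.
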